1.2 Study Agent(s) Background and Associated Known Toxicities

Pancreaze (pancrelipase) Delayed-Release Capsules is a combination of porcine-derived lipases, proteases, and amylases indicated for the treatment of exocrine pancreatic insufficiency due to cystic fibrosis, or other conditions.

Pancreatic-enzyme replacement therapy (PERT) is the standard of care to prevent maldigestion, malnutrition, and excessive weight loss in patients with exocrine pancreatic insufficiency (EPI) due to chronic pancreatitis (CP) or pancreatic surgery (PS). Pancreaze is available in dosages of 2,600, 4,200, 10,500, 16,800, and 21,000-lipase units per capsule.

1.3 Rationale

Pancrelipase has been approved for the use in patients with exocrine pancreatic insufficiency due to cystic fibrosis or other conditions. In randomized studies it has improved fat absorption and decreased the stool frequency in these patients. However, its utility in advanced pancreatic cancer patients has not been evaluated to date.

Advanced pancreatic adenocarcinoma is characterized by progressive weight loss and nutritional deterioration [27]. It is estimated that up to 80% of these patients present with cachexia [28]. This wasting has been linked not only to survival, but also to alterations in host defenses, functional ability, and quality of life [29]. There have been few studies of whether nutritional support improves outcomes for these patients and the results have been inconsistent [30, 31]. This is despite evidence that artificial nutrition can improve performance status and other outcomes in terminal cancer patients [32].

Exocrine pancreatic insufficiency (EPI), which results from tumor-induced damage to the pancreatic parenchyma, obstruction of the pancreatic duct, and surgical removal of pancreatic tissue, is considered a major cause of this syndrome[33]. This deficiency impairs the body's ability to absorb fat, carbohydrates, and proteins, which results in steatorrhea, abdominal cramps, weight loss, and malnutrition[34]. Associated symptoms include foul-smelling flatulence, diarrhea, greasy stools, abdominal discomfort following meals, pain, bloating, and belching[34]. EPI is estimated to

affect 68% to 92% of patients with pancreatic cancer prior to surgery and as many as 94% of those following surgery[35].

There are few effective therapies for pancreatic cancer and none for its associated cachexia. Megesterol and Marinol are routinely prescribed for appetite stimulation but not effective[36]. Therapies attempting diet modifications and supplements have also failed to improve outcomes[37].

One study randomized patients with pancreatic cancer to either 6 capsules of a high-dose pancreatic enzyme supplement per day or placebo for 8 weeks, with both groups receiving dietary counseling. Patients taking PERT gained 1.2% of their body weight compared with a 3.7% weight loss in the placebo group, with a mean difference in percentage of body weight change of 4.9% (P =.02; 95% confidence interval [CI] for the difference, 0.9%-8.9%). In addition, the fat absorption coefficient improved by 12% among those treated with PERT, while declining 8% for patients taking placebo (P =.13)[33].

Patients with borderline resectable, locally advanced, and advanced disease have distinct treatment paradigms and clinical outcomes. It is known that malabsorption is present in 68-92% of patients at diagnosis and most patients have associated symptoms [3, 6, 35, 38, 39]. In patients who had surgical resections, PERT was shown to improve the digestion of fat and associated symptoms of malabsorption [40]. As the cancer advances and the disease has spread to more area within the pancreas, the reliance on PERT is often increasingly recommended as the pancreas becomes less able to perform normal functions to aid in digestion of food. Previous studies have shown that lower trypsin, lipase and bicarbonate secretion are present in patients with non-resectable pancreatic cancer and pancreatic ductal obstruction [7]. As the utility of PERT varies with respect to each of the three cohorts of patients, it will be important to understand if there are some patient cohorts with an increased need for PERT.

1.4 Correlative Studies

In this prospective study, we will evaluate stool frequency and quality associated with the use of pancreatic enzyme replacement therapy. Recent evidence also suggests that gut microbial metabolites regulate the release of the gut hormones, which is associated with changes in gut microflora and its metabolic products [38, 39][38, 39]. In the last few years, several studies have presented substantial data suggesting a role for the oral and gut microbiota in pancreatic cancer [40]. In this context, the generation of germ-free mice has been extremely valuable to better understand the influence of the microbiome in carcinogenesis. In most models, these animals are less inclined to carcinogenesis, probably due to decreased tumor-associated inflammation [41]. The same profile is observed in antibiotic-treated mice that reduces the microbial load of the gut [42] Remarkably, bowel sterilization with broad-spectrum antibiotics appears to be protective in acute pancreatitis as well.

It would be important to better understand the microbiome associated with exocrine pancreatic insufficiency. We would also measure the changes in the microbiome as a response to the enzyme therapy.

We will also further explore the impact of this therapy on quality life, pain and patient reported outcomes in pancreatic cancer. We will utilize the PROMIS-29, and FACT-Hepatobiliary survey tools [43-45]. They are both validated in patients with pancreatic cancer and will help us understand the benefit of this therapy in our patient population.

Currently, the majority of information upon which oncologists base their treatment decisions is obtained at the time of the patient clinic visit. This data includes the patient's recall of symptoms and physical functioning, in addition to laboratory, imaging and physical exam information. Patient reported data (PRD) can be affected by recall bias [46, 47]. Furthermore, PRD can be influenced by a patient's desire to affect the physician's understanding of their clinical condition. For example,

patients may want their oncologist to believe that they are doing well, so that they may be a candidate for further cancer-directed therapies. Patients may de-emphasize physical symptoms and tolerance to therapy in an attempt to convince themselves that they are doing well. Oncologists rely on the PRD to make their own clinical judgments regarding changes in a patient's clinical condition and therapy choices.

The utilization of wearable biometric sensors may allow an inexpensive method of acquiring objective clinical data. Currently, off-the-shelf technology is being used commercially to track fitness. These wrist-worn devices can provide real-time data relating to movement, altitude, heart rate, body composition, temperature, and sleep quality. We will use the wearable activity monitor (e.g., Fitbit Charge HR) to assess activity in patients with pancreatic cancer and determine whether that activity correlates with changes in cachexia, functional status and PROs (i.e.PROMIS-29 and FAACT) around functional domains of quality of life [48-50]. Data collected may support the efficacy of this therapeutic intervention and influence the development of additional patient-centric, meaningful endpoints for future therapeutic trials around exocrine pancreatic insufficiency.

2.0 STUDY OBJECTIVES

2.1 Primary Objectives

2.1.1 Feasibility to complete pancreatic enzyme replacement therapy during the first 8 weeks of the study

2.2 Secondary Objectives

- 2.2.1 Measure weight stability at baseline and day 1 of every cycle for 6 months
- **2.2.2** Record 24-hour caloric intake at C1D1, C3D1, and end-of-study
- 2.2.3 Assess stool frequency at C1D1 and C3D1
- 2.2.4 Stool consistency at C1D1 and C3D1
- 2.2.5 Measurement of fat-soluble vitamins at baseline and end-of-study
- **2.2.6** Evaluate microbiome at C1D1 and C3D1
- 2.2.7 Determine if pancreatic enzyme replacement therapy is associated with increased daily activity (steps, counts, stairs, sleep, heart rate, active minutes) using a wristworn fitness tracker (e.g., Fitbit)

2.3 Patient-Reported Outcomes / Exploratory Objectives

- **2.3.1** To assess quality of life including pain assessment using PROMIS-29 at baseline and day 1 of every cycle for 6 months
- 2.3.2 To assess patient-reported response to therapy using FAACT (Functional Assessment of Anorexia/Cachexia Therapy) baseline and day 1 of every cycle for 6 months
- 2.3.3 Measure fecal elastase at baseline
- 2.3.4 Assess overall survival
- 2.3.5 Assess adverse events for safety and tolerability
- 2.3.6 Assess inflammatory biomarkers in research blood
- **2.3.7** Assess the presence of frailty phenotype
- **2.3.8** Assess body composition using computed tomography collected as standard of care every 8 weeks

2.4 Study Hypotheses

2.4.1 Primary Hypothesis

Pancreatic enzyme supplementation in addition to standard of care treatment is feasible for patients to follow for at least 8 weeks.

2.4.2 Secondary Hypotheses

Pancreatic enzyme supplementation in addition to standard of care treatment will stabilize weight loss in patients with borderline resectable, locally advanced, and advanced pancreatic cancer patients with exocrine pancreatic insufficiency.

Pancreatic enzyme supplementation, in addition to standard of care chemotherapy and dietitian consultation, will:

- Increase caloric intake
- Make stool frequency more consistent
- Improve stool consistency
- Improve levels of fat-soluble vitamins
- · Alter the microbiome favorably
- Increase daily activity

2.4.3 Exploratory Hypotheses

- Improve quality of life and symptoms of pain from baseline
- Patient-reported response the therapy will improve

- Fecal elastase may correlate with response to pancreatic enzyme supplementation
- Survival and response rate may benefit from a comprehensive approach to nutritional support
- Pancreatic enzyme supplementation will be safe and tolerable
- Weight loss and cachexia may be associated with genomic and stromal alterations in the tumor.
- · Inflammatory biomarkers may be improved
- The frailty phenotype may be improved
- Lean body mass may be maintained throughout treatment course

2.5 Endpoints

2.5.1 Primary endpoint

 Measure patient compliance to take pancreatic enzyme replacement therapy using a patient reported Pancreaze daily accountability log. Patient compliance will be defined as patients taking ≥ 50 % of the needed total lipase units. The primary endpoint will be met if at least 50% of the subjects in each cohort take at least 50% of the total needed lipase units within the first 8 weeks of treatment.

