5.3 Procedures During Treatment

These visits can occur within a window of -/+ 7 business days of the anticipated visit date to account for clinic closures or holidays and to align with the standard of care chemotherapy administration schedule.

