9.0 STATISTICAL CONSIDERATIONS

9.1 Power Assessment

The primary hypothesis to be tested is whether the percentage of patients who complete the course of pancreatic enzyme replacement therapy at 8 weeks is at least 50% for each of the three cancer stage subgroups: borderline resectable, locally advanced and advanced pancreatic cancer. We assumed a sample size equal to 10 patients for each group. The minimum detectable difference from the proportion 0.5 is 0.417 using a Binomial Exact test with Bonferroni correction. Thus, we will declare the sustainability of the therapy if 9 or more patients complete the treatment for each subgroup.

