9.2 Data Analysis Plan

The primary hypothesis to be tested is whether is the percentage of patients who complete the pancreatic enzyme replacement therapy at 8 weeks is at least 50% for each of the three cancer stage subgroups: borderline resectable, locally advanced and advanced pancreatic cancer. A 95% confidence interval [1] for the proportion of treatment completeness will be calculated for each cancer stage. The statistical analysis will be performed in three steps for all secondary endpoints: 1) Descriptive analysis: Measures of central tendency (mean, median and mode), measures of variability (standard deviation, range and quantiles). Standard distribution plots such as profiles-plots for repeated measures and box-plots will be constructed to examine the distribution of the data. 2) Univariable Analysis and 3) Multivariable analysis: The linear regression model will be applied to explain the secondary endpoints as a function of the patient's baseline variables. Assumptions of the linear regression model will be examined. If the assumptions are not met. Generalized Additive models for Location, Scale and Shape (GAMLSS) which provide a general framework for extending a standard linear model will be applied [2]. The goodness of fit for each model will be accessed through a residual analysis using Worm-plots [51] and variable selection will be performed as outlined by Harrell [4]. Random effects will be added to describe the repeated measures. In addition, overall survival curve will be estimated using the Kaplan-Meier method with 95% confidence interval. All tests of hypotheses will be two-sided and a significance level of 0.05 and calculations will be performed using R, version 3.2.3 [5].

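### Section 2.5.1 scores each patient on taking at least 50% of needed units, Sections 2.1 and 9 on completing therapy at 8 weeks; nothing links the two or fixes the denominator

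*Combined protocol and SAP*

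**What the plan says.** **Quantity.** Section 2.5.1 works from a patient-reported daily log and states: "Patient compliance will be defined as patients taking ≥ 50 % of the needed total lipase units". Its criterion for the cohorts reads: "at least 50% of the subjects in each cohort take at least 50% of the total needed lipase units within the first 8 weeks".

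**Completion.** The primary objective (2.1) is "Feasibility to complete pancreatic enzyme replacement therapy during the first 8 weeks of the study". The primary hypothesis (2.4.1) is that supplementation added to standard care "is feasible for patients to follow for at least 8 weeks". Section 9.1 tests "whether the percentage of patients who complete the course of pancreatic enzyme replacement therapy at 8 weeks is at least 50" per cent in each stage subgroup and concludes: "Thus, we will declare the sustainability of the therapy if 9 or more patients complete the treatment for each subgroup". Section 9.2 adds: "A 95% confidence interval [1] for the proportion of treatment completeness will be calculated for each cancer stage".

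**Denominator and analysis set.** Section 4.1.3 refers compliance to the recommended dose but names no period. Section 4.5 replaces subjects who withdraw from study treatment. The Study Summary allows up to 40 patients to obtain 30 evaluable ones. Evaluability is defined for toxicity (6.3.4) but not for the primary endpoint.

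**Data source.** Footnote 4 of the Time and Events Table (5.6) limits the diary to the first two cycles, with return when each is complete. Section 5.3 lets visits fall "within a window of -/+ 7 business days of the anticipated visit date", whereas the table header allows 7 days.

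**The concern.** This point is about who counts as a success. It is not about how many successes a cohort needs.

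Taking half the units and completing the course are different events unless the plan says otherwise, and it does not. A patient can take half of the 8-week quantity and then stop for good. A patient can also stay on the capsules throughout and take less than half.

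The exact test, the 9-of-10 rule and the confidence intervals in Section 9 all need a numerator, and the plan does not say which event supplies it. If the choice is made once the diaries have been read, the primary conclusion can depend on it. A result scored on quantity would also be reported under the language of completion and sustainability.

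**Working it through.** **Inputs.** Ten patients per cohort, null proportion 0.5, exact binomial test with Bonferroni correction, detectable difference 0.417 and the rule of 9 or more (9.1). A cycle is 28 days (4.1.3), so 8 weeks is 56 days. The threshold is 50% of needed units (2.5.1).

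**1. The plan's own figure.** The corrected level is 0.05/3 = 0.0167. Under p = 0.5, P(X ≥ 9 of 10) = 11/1024 = 0.0107, which is below 0.0167. P(X ≥ 8) = 56/1024 = 0.0547, which is not. Hence the rule of 9. Solving P(X ≥ 9 | p) = 0.80 gives p = 0.917, a difference of 0.417. The figure reproduces with a one-sided test and 80% power; the power is my assumption, as the plan states none. The arithmetic is the same whichever event is counted, so it cannot show which was meant.

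**2. Stopping early and still passing 2.5.1.** Assume constant daily need and a denominator fixed at 56 days. The number of meals and snacks then cancels. For a patient with adherence a who stops at day d:

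share = a × d / 56, so share ≥ 0.50 when d ≥ 28/a.

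| Adherence a | Share if stopped at day 28 | Earliest stop day that passes |
|---|---|---|
| 100% | 50.0% | 28 |
| 95% | 47.5% | 30 |
| 90% | 45.0% | 32 |
| 80% | 40.0% | 35 |
| 60% | 30.0% | 47 |
| 50% | 25.0% | 56 |

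Any patient with adherence above 50% who stops between day 28/a and day 56 meets 2.5.1 without staying on therapy for 8 weeks.

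**3. The reverse case.** A patient on therapy for all 56 days at 45% adherence has a share of 0.45 × 56/56 = 45% and fails 2.5.1. That patient would count under 9.1 if completing means remaining on therapy.

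**4. On-treatment denominator.** If need is counted only up to the stop day, share = a × d / d = a. Every stopper with adherence of at least 50% then passes, whatever the stop day.

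**5. What it could do to the decision (assumed rates).** Suppose 70% of patients complete and all of them take at least half their units. Suppose a further 10% to 20% stop early with at least half, and stoppers stay in the denominator. With P(X ≥ 9) = 10p⁹(1 − p) + p¹⁰:

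- completion counted, p = 0.70: 0.149
- quantity counted, p = 0.80: 0.376
- quantity counted, p = 0.90: 0.736

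These are per-cohort chances of reaching 9 of 10. The documents give no rates of completion or early stopping.

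**6. Diary window.** Seven business days are 9 or 11 calendar days, depending on the weekends crossed. If the diary ends at a Cycle 3 Day 1 visit held that early, it covers 47 or 45 of 56 days. With the table's 7 days it covers 49. If unrecorded days are scored as not taken (my assumption), a patient taking 60% scores:

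- 0.60 × 45/56 = 48.2% (fails)
- 0.60 × 47/56 = 50.4% (passes)
- 0.60 × 49/56 = 52.5% (passes)

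Only borderline patients change status.

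**The case against.** The best defence is that Section 2.5.1 is the only operational definition in the plan and that Section 9 merely uses completion as shorthand for it. The change log supports this: the primary endpoint was clarified at version 4. Treatment completeness in 9.2 can also be read as a quantity. A quantity threshold is a legitimate feasibility endpoint. This carries weight. The documents never define completing as being on drug at day 56, so a reader who takes Section 9 to mean persistence is inferring it. But the documents do not state the shorthand reading either, and the hypothesis of at least 8 weeks fits it poorly.

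Other stronger readings are also not supported:

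- **Anyone who stops at day 28 passes 2.5.1.** With a fixed denominator this needs every dose taken; at 95% adherence the share is 47.5%.
- **A patient who stops after a week can score 100%.** This needs an on-treatment denominator. Section 2.5.1 ties the units to the first 8 weeks, which favours a fixed period, although Section 4.1.3 does not settle it.
- **Early stoppers will inflate the count.** Section 4.5 may remove and replace them. Whether they stay in the primary analysis is unstated, so the direction of the effect is not known.
- **The diary window undermines the endpoint.** Nominally two cycles are exactly 56 days, and the example in step 6 changes status only near the threshold and under an assumed scoring rule.

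**Conclusion.** The point holds as an inconsistency in the patient-level primary outcome together with an unstated denominator. Two descriptions are in force, neither implies the other on its ordinary meaning, and nothing says which one feeds the test, the decision rule or the intervals.

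Assuming constant need and a fixed 56-day denominator, the two diverge for patients who stop between day 28/a and day 56, and the earliest such stop, day 28, requires perfect adherence. An on-treatment denominator would widen the gap. How many patients would be reclassified cannot be known from the documents; the probabilities in step 5 show only that the choice can matter. The mismatch between the visit windows is real but secondary.

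The separate conflict between half of the subjects (2.5.1) and 9 of 10 (9.1) as the cohort-level requirement is not part of this point and would remain after it is resolved.

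**What to change.** 1. In Sections 9.1 and 9.2, test and estimate the event that 2.5.1 defines: at least 50% of the units needed at the recommended dose. Bring the wording of the objective into line.
2. State that the denominator covers days 1-56 regardless of when the patient stops.
3. State that patients who stop treatment before day 56 stay in the primary analysis and are scored on this rule, and reconcile this with Section 4.5 and the Study Summary's evaluable patients.
4. Report the proportion still on therapy at day 56 as a separate descriptive figure. Requiring both persistence and quantity for success would create a third, stricter endpoint found in neither section; the inconsistency can be cured without it.
5. Lesser point: make the visit windows in Section 5.3 and the table in 5.6 agree, and have the diary cover days 1-56 whatever the date of the Cycle 3 Day 1 visit.

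The cost is wording and, for some patients, a few more diary days. Diaries of patients already past cycle 2 cannot be extended, so state how their unrecorded days are scored. The observed success rate may be slightly lower. The definition should be settled before the primary data are analysed.

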EOT End-of-Treatment FΑ Folinic Acid (Leucovorin) GLP-1 Glucagon-like peptide-1 H&P History & Physical Exam

HRPP Human Research Protections Program

IL1a Interleukin 1-alpha IV (or iv) Intravenously

MTD Maximum Tolerated Dose **LMF** Lipid Mobilizing Factors

LBM Lean Body Mass

NCI National Cancer Institute ORR Overall Response Rate

OS Overall Survival

PAWL Pancreatic Cancer-Associated Weight Loss

[figure not shown]
PBMCs Peripheral Blood Mononuclear Cells

PD Progression of Disease PFS Progression Free Survival

PR Partial Response

PYY Peptide YY

STUDY SCHEMA

Screening Phase

- 1. Informed consent
- 2. Screening
- 3. Eligibility review
- 4. Measure stool fecal elastase
- Measure fatsoluble vitamins

Treatment Phase

Cycle = 28 days

- 1. Measure weight stability
- 2. Assess 24-hour caloric intake
- 3. Assess stool frequency and consistency
- 4. Evaluate microbiome
- 5. Assess activity levels
- 6. Measure quality of life
- 7. Assess inflammatory biomarkers
- 8. Assess the presence of frailty phenotype
- 9. Assess body composition

End-of-Treatment

After C6D28:

- 1. Return pill bottles
- 2. Transition to Soc enzymes

Follow-up Phase

Safety evaluation

Measure fat-soluble vitamins

Survival

Optional sub-study: Followup activity tracking

STUDY SUMMARY

Title	Pancreatic-enzyme replacement therapy with pancreaze (pancrelipase) delayed-release in addition to standard of care for borderline resectable, locally advanced and advanced pancreatic adenocarcinoma patients (PANCAX-3) with cachexia and exocrine pancreatic insufficiency.		
Short Title	PANCAX-3		
Protocol Number	IIT2018-29-[name]-PNCX3		
Phase	Phase 2		
Methodology	Single arm, Single center		
Accrual Duration	18 months		
Study Duration	Approximately 6 months from screening to end of treatment assessment. Subjects will continue to be followed for survival for 36 months.		
Study Center(s)	Single-center, Cedars-Sinai Medical Center		
Objectives	 Feasibility to complete pancreatic enzyme replacement therapy at 8 weeks Measure weight stability at baseline and day 1 of every cycle for 6 months 24-hour caloric intake at baseline, C3D1, and end-of-study Stool frequency at baseline and C3D1 Quality of life assessment baseline and day 1 of every other cycle for 6 months Fitness tracking will be assessed with a wrist-worn wearable activity monitor (e.g., Fitbit Charge HR) continuously from day 1 of cycle 1 until the end of study visit. 		
Number of Subjects	Up to 40 patients (30 evaluable patients)		

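### The primary endpoint has two success rules, 5 of 10 per cohort in Section 2.5.1 and 9 of 10 in Section 9.1, and nothing says which governs

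*Combined protocol and SAP*

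**What the plan says.** **Section 2.1.1 (objective).** The primary objective is "Feasibility to complete pancreatic enzyme replacement therapy during the first 8 weeks of the study". It gives no threshold.

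**Section 2.5.1 (endpoint).** The patient-level variable comes from the daily accountability log: "Patient compliance will be defined as patients taking ≥ 50 % of the needed total lipase units". The trial-level rule follows: "The primary endpoint will be met if at least 50% of the subjects in each cohort take at least 50" per cent of those units within 8 weeks.

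**Section 9.1 (power).** The primary hypothesis is that the completion rate at 8 weeks is at least 50% in each of the three stage subgroups, with 10 patients assumed per group. "The minimum detectable difference from the proportion 0.5 is 0.417 using a Binomial Exact test with Bonferroni correction", and from this the section concludes that "we will declare the sustainability of the therapy if 9 or more patients complete the treatment for each subgroup".

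**Section 9.2 (analysis).** The 50% hypothesis is repeated. "A 95% confidence interval [1] for the proportion of treatment completeness will be calculated for each cancer stage". The section also states: "All tests of hypotheses will be two-sided and a significance level of 0.05". It gives no decision threshold.

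**Study Summary.** The sample size is given only as a total: up to 40 patients, of whom 30 are evaluable.

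**The concern.** Sections 2.5.1 and 9.1 each state when the trial succeeds on its primary question, for the same three cohorts, and the pass marks are far apart. A trial that follows its plan exactly could report success under one and failure under the other from the same data. Because no order of precedence is given, the choice could be made with the results in view.

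Two further gaps make the conflict harder to resolve by reading alone:

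- **The counted event.** Section 2.5.1 counts patients who took at least half of their lipase units. Sections 9.1 and 9.2 count patients who *complete* therapy and never define the word. Section 2.1.1 uses the same word for the objective, so the compliance variable is probably meant, but no sentence says so.
- **The test settings.** The cutoff of 9 does not follow from the two-sided testing in Section 9.2 combined with the Bonferroni correction in Section 9.1.

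**Working it through.** **Inputs.** n = 10 per cohort, three cohorts, reference rate 0.5, detectable difference 0.417, exact binomial test with Bonferroni correction (Section 9.1); two-sided 0.05 (Section 9.2); observed 50% bar (Section 2.5.1). Bonferroni over three cohorts gives 0.05/3 = 0.0167.

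**1. Reproducing the plan's figure.** With X ~ Binomial(10, 0.5):

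- P(X ≥ 8) = 56/1024 = 0.0547, above 0.0167.
- P(X ≥ 9) = 11/1024 = 0.0107, below 0.0167.

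The one-sided cutoff is therefore 9. Section 9.1 states no power; assuming 80%, solving P(X ≥ 9 | 10, p) = 0.80 gives p = 0.9167, a difference of 0.417. Power at 0.917 is 0.801. The plan's figure reproduces, but only with a one-sided test at 0.0167 or, equivalently for this cutoff, a two-sided test at 0.05 without Bonferroni.

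**2. The plan's stated settings together.** For 9 of 10 the two-sided p is 2 × 0.0107 = 0.0215, which is above 0.0167. For 10 of 10 it is 2/1024 = 0.0020. A two-sided Bonferroni test therefore needs 10 of 10.

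**3. The two pass marks.** Half of 10 is 5. Results of 5, 6, 7 or 8 meet Section 2.5.1 and fail Section 9.1. The exact (Clopper-Pearson) 95% intervals are:

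- 5/10: 18.7% to 81.3%
- 8/10: 44.4% to 97.5%
- 9/10: 55.5% to 99.7%

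**4. Probability of each conclusion.** Assumptions: both rules count the same event, 10 patients per cohort, independent cohorts, one common true rate, and all three cohorts must pass (both rules say *each*). The joint probability is the per-cohort probability cubed. Meeting the 9.1 rule implies meeting the 2.5.1 rule, so the probability of opposite conclusions is P(X ≥ 5)³ − P(X ≥ 9)³.

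| True rate | P(X ≥ 5) | P(X ≥ 9) | All three, 2.5.1 | All three, 9.1 | Opposite conclusions |
|---|---|---|---|---|---|
| 0.7 | 0.9527 | 0.1493 | 0.865 | 0.003 | 0.861 |
| 0.8 | 0.9936 | 0.3758 | 0.981 | 0.053 | 0.928 |
| 0.917 | 0.9999 | 0.8010 | 0.9998 | 0.514 | 0.486 |

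At a true rate of exactly 0.5, the 2.5.1 rule passes all three cohorts with probability 0.623³ = 0.242.

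**5. Cohort size.** The cutoff of 9 holds only for n = 10. Nine successes give a one-sided p of 0.0327 at n = 11 and 0.0730 at n = 12, both above 0.0167.

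**The case against.** The best reply is that the sections do different jobs: Section 2.5.1 names the target rate, and Section 9.1 gives the evidence needed to show that it is exceeded. Both use 50%, Section 9.1 derives 9 of 10 from a test against 50%, and the labels differ (endpoint met versus sustainability declared). That would be a sensible design, but it is not what is written. Section 2.5.1 says the endpoint is met when half of the subjects comply, which is a rule on the observed count, and nothing links it to a test. Section 9.1 opens by calling its test the primary hypothesis, so the different labels do not separate the two conclusions.

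Three smaller points have substance:

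- If all three cohorts must pass, each can be tested at full alpha without Bonferroni (an intersection-union test). Two-sided 0.05 then gives 9 of 10 (p = 0.0215), and only the Bonferroni wording is surplus. This is a valid repair, but the plan does not say it.
- If cohorts were judged separately, the rules would disagree in a given cohort with probability 0.803, 0.618 and 0.199 at true rates 0.7, 0.8 and 0.917. The conflict remains on that reading.
- Section 9.1 openly presents 10 per group as an assumption, so the dependence on cohort size is a secondary matter.

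**Conclusion.** The concern holds and must be fixed. The protocol contains two incompatible success rules for its primary endpoint and does not say which decides. Under the assumptions in step 4, they lead to opposite trial conclusions with probability 0.861, 0.928 and 0.486 at true rates of 0.7, 0.8 and 0.917. These figures also assume that *complete* means the Section 2.5.1 compliance variable; if it means something else, the two sections do not even count the same event. Separately, the 9-of-10 cutoff does not match a two-sided Bonferroni test, which would require 10 of 10.

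**What to change.** Use the Section 2.5.1 compliance variable in Sections 2.5.1, 9.1 and 9.2 in place of *complete* and *treatment completeness*. State which patients form each cohort's denominator, because Section 4.5 replaces patients who withdraw. Then keep one rule.

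**Option (a): exact test against 50%.** Delete the observed-50% sentence from Section 2.5.1 and state the test settings in both 9.1 and 9.2:

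- *One-sided at 0.05/3 per cohort*, as a declared exception to the two-sided statement in 9.2. Give the cutoff by actual cohort size: 8 of 8, 9 of 9, 9 of 10, 10 of 11, 11 of 12, 11 of 13. At n = 6 or 7 every patient must succeed (6 of 6: 1/64 = 0.0156; 7 of 7: 1/128 = 0.0078). No cutoff exists at 5 or fewer (5 of 5: 1/32 = 0.0313).
- *Two-sided at 0.05 without Bonferroni*, if success requires all three cohorts and the plan says so. The cutoff at n = 10 stays at 9.
- *Two-sided at 0.05/3*, with the cutoff at n = 10 changed to 10.

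The cost is a demanding bar. With 9 of 10, all three cohorts pass with probability 0.514 at a true rate of 0.917 and 0.053 at 0.8. With 10 of 10 these fall to 0.4204³ = 0.074 and 0.1074³ = 0.001.

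**Option (b): descriptive.** Keep the observed-50% bar, delete the test and the 9-of-10 rule, and report each cohort's proportion with an exact 95% interval. The cost is that 50% is no longer formally tested, a cohort passes at 5 of 10 with an interval of 18.7% to 81.3%, and Section 9.1 needs a new sample-size justification, for example one based on precision.

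The change is to wording only, but it alters the primary success rule, so it needs an amendment with IRB approval (Section 10.6.4). The sponsor should record its choice before the primary data are analysed. Because compliance is calculated as diaries are returned, the amendment should also say what was already known at that point.
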